###### Bilateral Cohort

For each MRI and strength parameter, descriptive statistics of the raw data as well as the absolute and percent change from baseline will be provided by side treated [left and right] as well as for the average of the left and right sides.

A one-sample t-test will be performed to estimate the effect of ACE-083 with corresponding 90% and 95% confidence intervals for the following variables: TMV percent change from baseline 3 weeks post last dose, CCMV percent change from baseline 3 weeks post last dose, FF absolute change from baseline 3 weeks post last dose, and percent change in ankle dorsiflexion MVIC 3 weeks post last dose.

The analysis described above will be performed using the data for the average absolute as well as the average percent change from baseline for the left and right sides.

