For unilateral dosing (part 1 only), if disease involvement in the lower leg or upper arm is asymmetric, the side that is weakest should be injected provided the MRC criterion is met. For bilateral dosing in Part 1, if only one side is weak (i.e., contralateral side is MRC grade 5), it is acceptable to enroll the patient and to inject only the weak side. If a patient meets inclusion criteria for both the TA and BB, the investigator will choose one target muscle based on the patient's clinical presentation as well as on cohort availability and ability to complete assessments for muscle volume (MRI), strength, and function.

In Cohorts 1 and 2 of Part 1, each dose will be administered unilaterally into the same targeted muscle, once every 3 weeks for up to 5 doses. For optional Cohort 3, bilateral dosing may be explored (to be determined by SRT), with a maximum absolute dose level of 250 mg/muscle administered bilaterally every 3 weeks for 5 doses.

For Part 2, ACE-083 or placebo (normal saline) will be administered every 3 weeks for approximately 6 months (9 doses). Patients who complete the double-blind treatment period will immediately roll over to open-label treatment of ACE-083, receiving the same dose of active drug, bilaterally in either the TA or BB muscle, once every three weeks for approximately 6 months (8 doses).

The planned dose scheme for Part 1 is below.

Part 1: N=Up to 36 (3-month, dose-escalation, non-randomized, open-label)

Cohort	Muscle	Dose Level ^a	ACE-083 n
1a	Tibialis anterior	150 mg	6
2a	Tibialis anterior	200 mg ^b	6
3a (optional)	Tibialis anterior	TBD ^b	6

^a Injection into muscle once every three weeks

^b Dose levels for Cohorts 2 and 3 to be determined by SRT, not to exceed 250 mg per muscle

Cohort	Muscle	Dose Level ^a	ACE-083 n
1b	Biceps brachii	150 mg	6
2b	Biceps brachii	200 mg ^b	6
3b (optional)	Biceps brachii	TBD ^b	6

The planned dose scheme for Part 2 is below.

Part 2: N=Up to 56^a (6-month, randomized, double-blind, placebo-controlled, with 6-month open-label extension)

6-month, double-blind, placebo-controlled				6-month, open-label extension		
Muscle	Dose Level ^b	ACE-083 n	Placebo n	Muscle	Dose Level ^b	ACE-083 n
Tibialis anterior	TBD ^c	14	14	Tibialis anterior	TBD ^c	28
Biceps brachii	TBD ^c	14	14	Biceps brachii	TBD ^c	28

^a N=14 active, 14 placebo per muscle.

^b Injection into muscle once every three weeks

^c Based on review of Part 1, not to exceed 250 mg per muscle

Individual Dose Modification Rules

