8. STUDY POPULATION

8.1. Inclusion Criteria

Patients are eligible to be included in the study only if they meet all of the following criteria at screening:

Inclusion Criteria:

1. Age \geq 18 years
2. Genetically-confirmed FSHD1 or FSHD2 (or a first-degree relative with genetically confirmed FSHD1 or FSHD2) and clinical findings meeting FSHD criteria
3. Part 1 TA cohorts:
 - a. 6-minute walk distance \geq 150 meters (without a brace)
 - b. Left and/or right ankle dorsiflexion Medical Research Council (MRC) manual muscle testing (MMT) grade 3 to 4+, inclusive ([Appendix 3](#))

Note: Contralateral side may be MRC MMT grade 3 to 5

Part 1 BB cohorts:

- a. Left and/or right elbow flexion MRC MMT grade 3 to 4+, inclusive ([Appendix 3](#))

Note: Contralateral side may be any MRC MMT grade

Part 2 TA cohorts:

- a. 6MWD \geq 150 and \leq 500 meters (without a brace); a maximum of 20% of enrolled patients with 6MWD \geq 450 meters will be included
- b. Left and right ankle dorsiflexion MRCMMT grade 3 to 4+, inclusive ([Appendix 3](#))

Part 2 BB cohorts:

- a. Left and right elbow flexion MRC MMT grade 3 to 4+, inclusive ([Appendix 3](#))
4. Females of childbearing potential (defined as sexually mature women who have not undergone hysterectomy or bilateral oophorectomy, or are not naturally postmenopausal \geq 24 consecutive months) must have negative urine pregnancy test prior to enrollment and use highly effective birth control methods (abstinence, oral contraceptives, barrier method with spermicide, or surgical sterilization) during study participation and for 8 weeks following the last dose of ACE-083. Hormonal birth control use must be stable for at least 14 days prior to Day 1. Males must agree to use a condom during any sexual contact with females of childbearing potential while participating in the study and for 8 weeks following the last dose of ACE-083, even if he has undergone a successful vasectomy. Patients must be counseled concerning measures to be used to prevent pregnancy prior to the first dose of ACE-083.

5. Ability to adhere to the study visit schedule/procedures, and to understand and comply with protocol requirements
6. Signed written informed consent

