10. TREATMENT OF PATIENTS

10.1. Treatments Administered

Using electromyography (EMG) or ultrasound guidance, each dose of study drug will be administered into the non-tendinous portion of the TA or BB as a series of up to 5 equal-volume injections. The use of EMG or ultrasound guidance will ensure that viable muscle is present at the injection site. If the degree of atrophy or fibro-fatty infiltration poses administration challenges, injections of ACE-083 should be distributed at least 2 cm apart into viable muscle. Injection site locations as well as measures to avoid adjacent nerves and blood vessels and prevent intravascular injection are outlined in the Investigational Product (IP) Handling Guide.

For unilateral dosing, if disease involvement in the lower leg or upper arm is asymmetric, the side that is weakest should be injected provided the MRC criterion is met. For bilateral dosing in Part 1, if only one side is weak (i.e., contralateral side is MRC grade 5), it is acceptable to enroll the patient and to inject only the weak side. If a patient meets inclusion criteria for both the TA and BB, the investigator will choose one target muscle based on the patient's clinical presentation as well as on cohort availability and ability to complete assessments for muscle volume (MRI), strength, and function.

In Part 1, Cohorts 1 and 2, each dose will be administered unilaterally into the same targeted muscle, once every 3 weeks for up to 5 doses. For optional Cohort 3, bilateral dosing may be explored (determined by SRT), with a maximum absolute dose level of 250 mg/muscle administered bilaterally, every 3 weeks for 5 doses.

For Part 2, ACE-083 or placebo (normal saline) will be administered every 3 weeks for approximately 6 months (9 doses). Patients who complete the double-blind treatment period will immediately roll over to open-label treatment of ACE-083, receiving the same dose of active drug, bilaterally in either the TA or BB muscle, once every three weeks for approximately 6 months (8 doses).

The planned dose scheme for Part 1 and 2 is shown below.

Table 4: Cohort Schedule for Study A083-02**Part 1: N= Up to 36 (3-month, dose-escalation, non-randomized, open-label)**

Cohort	Muscle	Dose Level ^a	ACE-083 n
1a	Tibialis anterior	150 mg	6
2a	Tibialis anterior	200 mg ^b	6
3a (optional)	Tibialis anterior	TBD ^b	6

Cohort	Muscle	Dose Level ^a	ACE-083 n
1b	Biceps brachii	150 mg	6
2b	Biceps brachii	200 mg ^b	6
3b (optional)	Biceps brachii	TBD ^b	6

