#### 4.1.1. Sample Size Determination

There was no formal sample size calculation for Part 1. Six patients in each cohort will provide sufficient data to evaluate safety and a preliminary assessment of changes in muscle volume and muscle strength.

The sample size calculation for Part 2 is based upon the percent change from baseline in total muscle volume of the injected TA muscle 3 weeks after the last dose. A 10% difference between ACE-083-treated and placebo groups in the percent change in total muscle volume from baseline is considered to be clinically meaningful. The standard deviation (SD) is assumed to be approximately 9% for each group, based on preliminary MRI data for the ACE-083-treated side from the initial TA cohort in Part 1. Similar assumptions apply for the treatment of the BB muscle.

Assuming a 2-sided type I error rate of 0.10, a 10% difference in percent change from baseline between ACE-083-treated and placebo groups in total muscle volume, a standard deviation of 9% for each group, and a 1:1 randomization, 83% power is achieved with a total sample size of 24 for the TA muscle (12 active, 12 placebo), based on a standard t-test.

In addition, this sample size also provides 83% power to detect a 10% difference in 6-minute walk test distance, based on a similar estimated SD of 9% and a 2-sided type 1 error rate of 0.10.

In order to account for dropouts (up to 15%), 28 patients will be randomized to study treatment for each muscle (14 active, 14 placebo) to ensure that at least 12 patients per treatment group complete the double-blind treatment period.

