#### 4.1.3. Treatment Description

Treatment descriptions as well as abbreviations used in tables, listings, and figures are described below:

##### Part 1

Unless otherwise stated, tables and figures will be presented as shown below:

Part 1 – Tibialis Anterior

ACE-083 150 mg Unilateral	ACE-083 200 mg Unilateral	ACE-083 200 mg Bilateral	Overall
------------------------------	------------------------------	-----------------------------	---------

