Additional techniques for handling missing data may also be considered and evaluated.

- If a patient has a Day 190 assessment performed after having received the Day 190 dose (first dose in the open-label phase), then the Day 190 assessment for that patient will be included in statistical analyses of Day 190 data only if the difference between the Day 190 assessment and the Day 190 dose date is less than or equal to 7 days.
- Descriptive statistics for quantitative parameters will be provided using number of observations (N), mean, standard deviation (SD), standard error of the mean (SEM), median, minimum and maximum;
- Should it be necessary to convert duration in days to duration in months, the duration in days will be divided by 30.417 (365/12) to calculate duration in months.
- Descriptive statistics for qualitative parameters will be provided using frequencies (N) and percentages (%).
- If the result of a continuous variable contains nonnumeric values (e.g. ‘<X’ or ‘>X’), the imputed values used for the descriptive statistics will be determined by considering the following rules:
  - If the value is ‘<X’, the value used will be X/2;
  - If the value is ‘>X’, the value used will be X.
- Concerning the determination of absolute and percent change from baseline for data such as MRI and muscle strength where assessments are reported separately for the left and right sides and the average absolute and/or percent change from baseline is needed, the absolute and/or percent change is determined for the left and right sides separately and then averaged. The “average” represents the “average” absolute (or percent) change from baseline for the left and right sides. For MRI and muscle strength data, should a patient have an MRI and/or strength assessment on one side (i.e. right side) but not the other side at an individual timepoint, the value for the average absolute (or percent) change from baseline for that patient and timepoint will be the absolute (or percent) change from the side from which the MRI and/or strength assessment was obtained.

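### In the Part 1 bilateral cohort a patient may be injected on one side only, but the effect is estimated from the left-right average, so an uninjected muscle would dilute it

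*SAP*

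**What the plan says.** For bilateral dosing in Part 1, the condition in the Protocol Synopsis, repeated in Protocol 10.1, begins "For bilateral dosing in Part 1, if only one side is weak (i.e., contralateral side is MRC grade 5". The permission follows: "it is acceptable to enroll the patient and to inject only the weak side". Protocol 8.1 makes the case reachable for the tibialis anterior (TA) cohorts: "Note: Contralateral side may be MRC MMT grade 3 to 5".

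SAP Table 1 has one bilateral Part 1 cohort, 3a (TA, n=6), labelled "ACE-083 200 mg Bilateral" in SAP 4.1.3. Cohort 3b is unilateral. For the bilateral cohort, SAP 4.7.2.1 states: "A one-sample t-test will be performed to estimate the effect of ACE-083 with corresponding 90% and 95% confidence intervals". The variables are total muscle volume, calculated contractile muscle volume, fat fraction and ankle dorsiflexion strength, each three weeks after the last dose. The analysis is done "using the data for the average absolute as well as the average percent change from baseline for the left and right sides".

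SAP 4.1.5 defines the average: "the absolute and/or percent change is determined for the left and right sides separately and then averaged". Its one exception is a side with no assessment at that timepoint. SAP 4.7.1.2 assigns treated, untreated and treated-minus-untreated values to unilateral dose cohorts, and left, right and average values to bilateral dose cohorts.

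SAP section 6 (Unilateral vs. Bilateral, Part 1) describes laterality by what the patient receives, and identifies the treated side of unilaterally dosed patients from the dosing datasets.

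**The concern.** The Part 1 secondary objectives (Protocol Table 3, SAP 2.2) concern volume, fat fraction and strength of the injected muscle. A patient in cohort 3a who is injected on one side still has data on both: the MRI is bilateral, and strength is tested on both sides at all visits (Protocol Table 5 and its footnote 11). The missing-side exception in SAP 4.1.5 would therefore not normally apply, and the uninjected muscle would count for half of that patient's value.

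The SAP avoids this in the unilateral cohorts, where the treated side is analysed separately. It has no matching rule for the one cohort type in which the protocol allows one-side and two-side injection to be mixed. At stake is the size of the effect estimate in the only Part 1 cohort that gives bilateral data before Part 2, where dosing is bilateral.

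**Working it through.** The plan gives no Part 1 figure to reproduce. SAP 4.1.1 reports no formal calculation for Part 1 and says only "Six patients in each cohort will provide sufficient data to evaluate safety" and a preliminary look at volume and strength. The following illustrates the dilution.

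**Inputs**
- n = 6 patients in cohort 3a (SAP Table 1).
- k = number injected on one side. Not in the documents; assumed 1 to 3.
- E = mean percent change in an injected muscle. Illustrated at 10, the Part 2 planning difference for TA volume (SAP 4.1.1), and at 15, the approximate Phase 1 gain in the rectus femoris of healthy postmenopausal women (Protocol 7.2).
- U = mean percent change in an uninjected muscle. Not in the documents; assumed 0 or 2.

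**Formula**

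A patient injected on both sides contributes E. A patient injected on one side contributes (E + U)/2. So

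expected cohort mean = [(6 − k)E + k(E + U)/2]/6 = E − k(E − U)/12.

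With U = 0, each such patient lowers the mean by E/12, which is 8.3% of the effect: 10/12 = 0.83 points, or 15/12 = 1.25 points.

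| E | U | k = 1 | k = 2 | k = 3 |
|---|---|---|---|---|
| 10 | 0 | 9.17 | 8.33 | 7.50 |
| 10 | 2 | 9.33 | 8.67 | 8.00 |
| 15 | 0 | 13.75 | 12.50 | 11.25 |
| 15 | 2 | 13.92 | 12.83 | 11.75 |

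Using only the injected side for those patients returns E in every row.

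**Set against the precision of six patients**

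Borrowing the 9% SD from SAP 4.1.1, the standard error is 9/√6 = 3.67 points. The half-width of a 90% interval is 2.015 × 3.67 = 7.4 points (t with 5 degrees of freedom). The SD of a two-side average could be smaller than 9%.

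**Interval coverage by simulation**

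Settings: n = 6, E = 10, U = 0, SD 9 per side, within-patient correlation 0, 0.5 and 0.8, with 100,000 runs each. Coverage of the true 10 by the nominal 90% interval on the left-right average was:
- k = 1: about 90%
- k = 2: 87.4% to 88.4%
- k = 3: 82.1% to 85.3%

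With injected sides only, coverage stayed between 89.9% and 90.4% throughout.

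**The case against.** The strongest reply is SAP section 6. It describes unilateral and bilateral treatment by what the patient actually receives, so a cohort 3a patient injected on one side could be read as unilaterally treated, with the treated side taken from the dosing data. That is a real mitigation, and it shows that the fix needs no new data. It does not close the gap. The section sets no analysis rule, while SAP 4.7.1.2 and 4.7.2.1 assign the left-right average by cohort and do not refer to it. The list of modifications in SAP section 5 does not mention the case either.

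The other objections limit the point:
- **No one is shown to be affected.** The protocol calls one-side injection acceptable; nothing says that it happened. A reader might infer that the cohort 3a estimate is biased. The documents do not support that: with k = 0 there is no dilution.
- **No decision depends on this analysis.** A reader might infer that a diluted estimate would distort the Part 2 dose or muscle choice. Part 1 efficacy data are reviewed before Part 2 (Protocol 7.1 and 14.2), but no rule ties that choice to this t-test, and the Safety Review Team also makes recommendations.
- **It is not framed as a hypothesis test.** The SAP uses the one-sample t-test for estimates and intervals, and states no null value or significance level for it.
- **The data will be visible.** By-side summaries, individual listings (SAP 4.1.5) and dosing listings (SAP 4.6.1) are planned, so a reader could find such patients. Left and right summaries do not in themselves separate injected from uninjected muscles, and the wording about the side treated belongs to the descriptive statistics, not to the t-test.

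**Conclusion.** The gap is real but small and conditional. Following the SAP as worded, any cohort 3a patient injected on one side would bring an uninjected muscle into an effect meant for the injected one. If that muscle does not change, each such patient costs 8.3% of the effect: 0.83 points at the 10% planning difference, or 1.25 points at 15%, a figure from another muscle and a healthy population. If the uninjected muscle gains 2%, the loss at E = 10 is (10 − 2)/12 = 0.67 points. One such patient leaves 90% interval coverage near nominal under the simulated settings; two or three would erode it. The number of such patients and the behaviour of uninjected muscle are assumptions throughout.

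The effect is confined to a secondary Part 1 estimate in six patients. The Part 2 primary analysis is not affected: Part 2 eligibility requires grade 3 to 4+ on both sides (Protocol 8.1), and the one-side allowance is written for Part 1. This is a minor clarification.

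**What to change.** In SAP 4.1.5 and in the Bilateral Cohort part of 4.7.2.1, state that the patient-level value in the bilateral cohort is the mean over injected sides only, with injected sides identified from the dosing data as in SAP section 6. Report how many cohort 3a patients were injected on one side; if there were none, saying so closes the point.

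The cost is one sentence in each place and one count in the report. The side dosed is already to be read from the dosing datasets, so no data collection changes.

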### **Motor Function Variables**

Individual motor function data will be listed.

For motor function test variables (TA cohorts: cumulative distance at 6 minutes from the 6-minute walk test, time to complete 10 meter walk/run test, 4-stair ascend time, 4-stair descend time, gait parameters; BB cohorts: PUL parameters) the raw data as well as absolute and percent change from baseline will be provided.

Least square mean estimates of the effect of ACE-083 and corresponding 90% and 95% confidence intervals will be produced for the percent change data at 3 weeks post last dose described above using an ANCOVA with BASELINE, COHORT, and BASELINE\* COHORT as covariates where:

- BASELINE represents the baseline value of the parameter of interest
- COHORT represents the dose level of ACE-083 administered to the muscle
- BASELINE\*COHORT represents the interaction of BASELINE and COHORT

Additional analyses may be performed as appropriate.

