5.2. Study Rationale

The initial proposed indication for ACE-083 is facioscapulohumeral muscular dystrophy (FSHD), which is the third most common muscular dystrophy and has an autosomal dominant pattern of inheritance in most patients compared to a less common sporadic form which affects approximately 10-30% of patients.^{6,7} FSHD has a prevalence of 1:15,000-1:20,000.^{6,7} FSHD is characterized by complex genetic mechanisms relating to the double homeobox protein 4 gene (DUX4). DUX4 is normally repressed through epigenetic mechanisms in somatic cells and is derepressed in FSHD leading to toxic damage to skeletal muscle cells. The DUX4 gene is located in the D4Z4 microsatellite array in the 4q35 region. In FSHD1, one D4Z4 allele is contracted (1 to 10 repeat units) and has been associated with DNA hypomethylation and chromatin structural changes. FSHD2 accounts for about 5% of FSHD cases and has been characterized by hypomethylation of both normal D4Z4 alleles. Mutations in the SMCHD1 gene resulting in changes in the D4Z4 chromatin structure have been linked to FSHD2. Both types are phenotypically indistinguishable.⁸ Other rare atypical variants of the disease can also manifest in the setting of a genetic diagnosis.

FSHD patients typically present in their second decade of life and live a normal lifespan. The disease is clinically characterized by slowly progressive focal asymmetric areas of muscle weakness involving the facial, scapular, upper arm, lower leg, and abdominal muscles. Biceps and triceps involvement can affect upper arm flexion and extension limiting ability to lift objects and perform activities of daily living. Weakness of the tibialis anterior (TA), a commonly affected lower extremity muscle in FSHD patients, often results in impaired dorsiflexion and foot drop. Foot drop can lead to gait instability and falls requiring the use of braces, walking devices, and wheelchairs. About 20% of FSHD patients become non-ambulatory. Other clinical complications associated with FSHD may involve respiratory muscle weakness, resulting in pulmonary complications, retinovascular disease, chronic pain, and hearing loss.⁹ Laboratory and muscle biopsy findings are often non-specific and therefore are not required for diagnosis. Elevations in creatine kinase (CK) can be seen but are often normal in asymptomatic patients. Muscle biopsy can show variable changes in muscle fiber size (both hypertrophy and atrophy) and inflammatory cellular infiltrates.¹⁰

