  - General measures: Ambulation distance (meters), Ambulation time (ms), Ambulation velocity (cm/s), Mean normalized velocity (Leg lengths/s), Number of steps, Cadence (steps/min.), Step time differential (ms), Step length differential (m), Cycle time differential (ms), Forward lean (deg.), Sway (m), Left step time (ms), Left Cycle Time (ms), Left Step Length (m), Left stride length (m), Left base width (m), Left single support (% gait cycle), Left initial double support (% gait cycle), Left terminal double support (% gait cycle), Left total double support (% gait cycle), Left swing (% gait cycle), Left stance (% gait cycle), Left step extremity ratio (ratio), Right step time (ms), Right Cycle Time (ms), Right Step Length (m), Right stride length (m), Right base width (m), Right single support (% gait cycle), Right initial double support (% gait cycle), Right terminal double support (% gait cycle), Right total double support (% gait cycle), Right swing (% gait cycle), Right stance (% gait cycle), Right step extremity ratio (ratio)
  - Initial measures: Initial left hip flexion (deg.), initial left knee flexion (deg.), initial left ankle dorsiflexion (deg.), initial left clearance (cm), Initial right hip flexion (deg.), initial right knee flexion (deg.), initial right ankle dorsiflexion (deg.), initial right clearance (cm)
  - Peak measures: Peak left hip min (deg.), Peak left hip max (deg.), Peak left knee min (deg.), Peak left knee max (deg.), Peak left ankle dorsiflexion min (deg.), Peak left ankle dorsiflexion max (deg.), Peak left clearance max (cm.), Peak right hip min (deg.), Peak right hip max (deg.), Peak right knee min (deg.), Peak right knee max (deg.), Peak right ankle dorsiflexion min (deg.), Peak right ankle dorsiflexion max (deg.), Peak right clearance max (cm.)
  - Average measures: Average left hip min (deg.), Average left hip max (deg.), Average left knee min (deg.), Average left knee max (deg.), Average left ankle dorsiflexion min (deg.), Average left ankle dorsiflexion max (deg.), Average left clearance max (cm.), Average right hip min (deg.), Average right hip max (deg.), Average right knee min (deg.), Average right knee max (deg.), Average right ankle dorsiflexion min (deg.), Average right ankle dorsiflexion max (deg.), Average right clearance max (cm.)
- 100-meter timed test (patients receiving ACE-083 in the TA muscle during the Part 2 open-label phase)

- Time to complete 100-meters (sec.)

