#### **4.7.2.3. Part 2 Open-Label Extension**

Individual data will be listed. The listing of such data will be collated with the data collected in the double-blind, placebo-controlled phase.

Descriptive statistics will be provided for raw data and changes (percent and absolute change) from the start of the open-label extension (Day 190) will be provided by treatment sequence for each scheduled time. The treatment sequence refers to the treatment sequence from double-blind to open label (i.e. ACE-083 □ ACE-083 or Placebo □ ACE-083). For MRI and strength data, such summaries will be provided by scheduled time for each side treated as well as the average of the left and right sides.

Additional analyses may be performed as appropriate.

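### The SAP puts the Part 1 gait effect estimates on percent change, which does not suit angles and differentials, and its separate gait text leaves unclear whether those estimates are planned at all

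*SAP*

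**What the plan says.** SAP 4.7.2.1, under Motor Function Variables, closes its list of Part 1 tests with "4-stair descend time, gait parameters; BB cohorts: PUL parameters) the raw data as well as absolute and percent change from baseline will be provided". The next paragraph says: "Least square mean estimates of the effect of ACE-083 and corresponding 90% and 95% confidence intervals will be produced for the percent change data". The time point is three weeks after the last dose, and the model terms are baseline, cohort and their interaction. Gait is not excluded, and no least-squares mean is planned on absolute change.

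Further on in 4.7.2.1, the text headed Gait plans listings, averaging of triplicates, a derived stride length and descriptive statistics. It mentions neither an ANCOVA nor percent change, and it does not say that the earlier paragraph excludes gait.

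The gait variables are listed in SAP 4.7.1.3.1. They include "Step time differential (ms), Step length differential (m), Cycle time differential (ms), Forward lean (deg.), Sway (m" and joint angles such as "initial left ankle dorsiflexion (deg.), initial left clearance (cm". SAP 4.1.4 sets the gait baseline as the mean of the available pre-dose values, of which there are up to three. Neither 4.1.4 nor 4.1.5 has a rule for a zero or negative baseline.

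Protocol section 6 (Table 3) makes percent change the Part 1 exploratory endpoint for function, and Protocol 12.4 counts gait analysis among the motor function tests. Protocol 14.2.3.3 says that Part 1 function data are summarized descriptively.

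**The concern.** Percent change divides by the baseline. That works for a quantity that is always positive and has a true zero, such as velocity or step length. A joint angle has a zero set by convention, and its baseline can be negative. A differential, read here as a left-right difference because the SAP does not define it, can sit close to zero.

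The ankle angles bear directly on the treated muscle. Protocol 5.2 says that TA weakness "often results in impaired dorsiflexion and foot drop", so low dorsiflexion angles are plausible in these patients. If some baselines are negative or near zero, the Part 1 effect estimates for those variables could have the wrong sign, or could be set by one patient in a cohort of six.

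**Working it through.** **1. No figure to reproduce.** The documents give no gait values and no worked example, so the check is a count and the percent-change arithmetic.

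**2. Count of gait variables (SAP 4.7.1.3.1).**

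| Group | Variables | Joint angles | Forward lean | Differentials |
|---|---|---|---|---|
| General | 35 | 0 | 1 | 3 |
| Initial | 8 | 6 | 0 | 0 |
| Peak | 14 | 12 | 0 | 0 |
| Average | 14 | 12 | 0 | 0 |
| Total | 71 | 30 | 1 | 3 |

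Angles and differentials together: 30 + 1 + 3 = 34, and 34/71 = 47.9%. Ten of the 30 joint angles are ankle dorsiflexion (2 initial, 4 peak, 4 average).

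**3. Percent change.** The SAP prints no formula, so I use the usual 100 × (post − baseline)/baseline.

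| Baseline (deg) | Post (deg) | Absolute change | Percent change |
|---|---|---|---|
| -10 | -5 | +5 | 5/(-10) = -50% |
| -10 | -15 | -5 | -5/(-10) = +50% |
| -1 | +2 | +3 | 3/(-1) = -300% |
| +0.5 | +3.5 | +3 | 3/0.5 = +600% |
| +20 | +23 | +3 | 3/20 = +15% |
| 0 | +3 | +3 | undefined |

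The same gain of 3 degrees is reported as anything from -300% to +600% in these rows. Dividing by the size of the baseline without its sign would remove the reversal, but not the explosion or the undefined value.

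**4. Whether the model repairs this.** Baseline enters linearly, with a separate slope per cohort through the interaction. Percent change varies as 1/baseline, which a straight line cannot follow across zero. Each TA cohort has six planned patients (SAP Table 1).

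**5. Illustration on assumed baselines.** Cohorts of 6, true gain +3 degrees, SD of change 2, baseline SD 5, 20,000 simulated cohorts. All inputs except the cohort size are assumptions.

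| Mean baseline (deg) | Cohort mean percent change negative | 5th to 95th percentile |
|---|---|---|
| -5 | 75% | -356% to +243% |
| 0 | 50% | -499% to +474% |
| +5 | 25% | -247% to +337% |
| +20 | 0% | +8% to +25% |
| +60 | 0% | +3% to +7% |

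The mean absolute change had the wrong sign in at most 0.02% of cohorts in every row. These are unadjusted cohort means. The planned ANCOVA least-squares means and their intervals were not simulated.

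**6. How many variables are exposed.** If the 8 hip and knee maxima (4 peak, 4 average) stay well above zero, 30 + 3 − 8 = 25 of 71 (35%) remain, or 26 with forward lean.

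**The case against.** The strongest reply is that the dedicated Gait text governs. It is the more specific passage and is descriptive only. The Part 2 double-blind Gait text is descriptive too, and Protocol 14.2.3.3 points the same way for Part 1 function. This is a reasonable reading, but the SAP does not state it: the motor function paragraph names gait and is never withdrawn. Even on this reading, that paragraph still provides a descriptive percent change for gait.

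The second reply is that the safe scale is already planned. Raw data and absolute change are summarized for the same variables, so a reader can see the direction in degrees. That stands, and it limits the harm to the percent-change columns and the least-squares means built on them.

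A reader might infer that all 34 variables will give reversed or exploding results. The documents do not support that. They give no gait baselines and no sign conventions, and the failure needs a baseline that is negative or near zero. The illustration shows no reversal at mean baselines of +20 or +60 degrees. Differentials recorded as magnitudes cannot be negative, though they can still be near zero.

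A reader might also carry the point over to the open-label models. SAP 4.7.2.3 says: "Descriptive statistics will be provided for raw data and changes (percent and absolute change) from the start of the open-label extension (Day 190". That is descriptive, gives absolute change as well, and does not name gait. The open-label ANCOVA lists also leave gait out.

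**Conclusion.** Wrong as written, of minor severity. SAP 4.7.2.1 names gait among the variables whose Part 1 effect is estimated on percent change only, and the Gait text in the same section neither confirms nor cancels this. For 34 of the 71 gait variables percent change is an unsuitable scale. For any of them with a negative, near-zero or zero baseline, the stated rule gives a reversed, inflated or undefined value.

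The arithmetic follows from the usual percent-change formula. The number of variables affected in practice does not follow from the documents. About 25 of 71 is an estimate that rests on hip and knee maxima staying well above zero.

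The reach is limited to the exploratory Part 1 gait estimates, and to the open-label percent-change summaries if gait is included there. It would go too far to say that the Part 1 gait results as a whole cannot be interpreted, because absolute change is reported alongside. No gait variable is named as a basis for dose escalation or sample size.

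**What to change.** - Reconcile the Motor Function Variables and Gait texts in SAP 4.7.2.1 by stating whether gait is in the ANCOVA.
- If it is, model absolute change for the 30 joint angles, forward lean and the three differentials.
- Omit percent change for these 34 variables in the Part 1 gait summaries and in any open-label gait summaries under SAP 4.7.2.3. Keep it for strictly positive ratio-scale measures such as velocity, cadence, and step and stride length.
- List the change in SAP section 5, because Protocol Table 3 sets percent change as the functional endpoint.

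The cost is SAP wording, a variable list and one entry in section 5. No new data or derivations are needed, since absolute change is already planned for gait. There is a precedent in the same section: Part 1 fat fraction and FSHD-HI are estimated on absolute change. The downside is that effects on these variables are in degrees, milliseconds or metres and cannot be set directly beside the percent-change endpoints.
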